Design features (clinical trial / retrospective study / case) sample size, determination of the number of centers, study duration, if any randomization method and its importance Blindness method and its importance, if any	This study was planned as a randomized controlled experimental study. Computer-assisted randomization will be used to create groups (https://www.randomizer.org/). To determine the sample size, power analysis was performed using the $G^*$ Power (v3. 1.9) program. The power of the study is expressed as 1- $\beta$ ( $\beta$ = probability of type II error), and in general, studies must have 80% power. According to Cohen's (1988) effect size coefficients; Assuming that the evaluations to be made between two independent groups would have a medium effect size (d = 0.5), it was determined that there should be at least 64 people in each group, according to the calculation made using the t test.
Address of the clinic, laboratory, other medical units and institutions, if any, from cases, processing of data/keeping records, evaluation criteria, quality control and quality assurance	No samples will be taken from the babies forming the sample group.
Statistical method to be applied	The data obtained in the study were compiled using SPSS (Statistical Package for Social Sciences ) for Windows 25.0 program. In evaluating the data; Descriptive statistical methods will be used for number, percentage, min-max, mean and standard deviation values.  The compliance of the obtained data with normal distribution will be tested. Compliance with normal distribution can be examined with the QQ Plot drawing (Chan, 2003:280-285). In addition, normal distribution of the data used depends on the skewness and kurtosis values being between ±3 (Shao, 2002).  In normally distributed data, when comparing quantitative data, independent t test will be applied for the difference between two independent groups, when comparing two dependent stages, dependent t test will be applied, and when comparing more than two dependent stages, analysis of variance in repeated measurements (MIX ANOVA) will be applied and in case of a difference, Bonferroni will be applied to determine the group that makes the difference. will be used. Chi square analysis will be used to test the relationship between categorical variables.

- Kuller, J. M. (2014). Update on newborn bathing \_ newborn oath baby Nursing Reviews, 14(4), 166-170.

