TR Istanbul University-Cerrahpaşa ID: İstanbul UCEdu

Statistical Analysis Plan: June 1, 2023 The effect of two different bathing methods on vital parameters and stress levels in preterm babies.

Clinical Trial Number: NCT06166485

BIOSTATISTICS PRELIMINARY ASSESSMENT

The thesis summary and research hypotheses of the thesis titled "The effect of bathing applied in two different orders on the stress level and physiological parameters in term babies" were examined in detail. For this purpose, mothers who applied to the gynecology clinic of Istanbul Şişli Hamidiye Etfal Training and Research Hospital, whose weight was between 2.5 and 4 kg, whose Apgar score was over 7 points, who did not have any health problems, who were healthy term babies, and who voluntarily agreed to participate in the study. and their children will be included. As a data collection tool;

- Personal information form,
- Processing time (time to get the bath done),
- Babies' calm down time,
- newborn stress scale,
- Physiological parameters (body temperature, pulse, respiration, O2 saturation) will be used.

Data from IBM SPSS Statistics Standard Concurrent User V 26 (IBM Corp. , Armonk , New York, USA) will be evaluated in the statistical package program. Descriptive statistics will be given as number of units (n), percentage (%), mean \pm standard deviation ($Mean\pm SD$), median (M), minimum (min) and maximum (max) values. Shapiro-Wilk normality test will be used to ensure that numerical variables comply with normal distribution. The appropriate hypothesis testing method planned to be used in the study was determined as "Mixed Pattern Variance Analysis" if parametric test assumptions were met. In cases where the parametric test assumptions regarding the relevant test are not met, whether there is a difference between the groups in terms of quantitative variables will be evaluated with the "Student t test" if the parametric test assumptions are met, and with the "Mann-Whitney test" if the parametric test assumptions are not met. In examining whether the quantitative variables change according to the pre-test and post-test measurement time, they will be examined with the "Paired t test" if the test assumptions are met, and with the "Wilcoxon test" if they are not met. In all hypothesis tests, the probability of Type I error will be taken as α =0.05 and a value of p<0.05 will be considered statistically significant.

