Mohamed et al. $(2018)^{**}$ in their study, they investigated whether bathing applied in two different orders in term babies had an effect on stress level and physiological parameters. Differences between and within groups were calculated for body temperature (°C), heart rate (beats/ min) and oxygen saturation (%). Minimal significant change was observed in the study While the average heart rate (beats/ min) was 145 ± 16.44 points in the training group as a result of the first measurements, it was found to be 138 ± 12.12 points in the last measurement. In the control group, the first measurement was 140 ± 14.22 points and the last measurement was 139 ± 10.88 points. As a result, it was determined that there should be 86 observations in the sample with a statistical power level of 80.4% and a significance level of 5% for the calculated (f=0.128)* effect size. Considering sample loss (10%) such as dropping out of the study, it will be sufficient to work with at least 94 patients. The study was planned to include 47 people in each group.

^{*} COHEN, J., "Statistical Power Analysis for the Behavioral Sciences (Revised ed.)", 1977.

F tests - ANOVA: Repeated measures , within-between interaction

Analysis: A priori : Compute required sample size

Input: Effect size f=0.1275153

> α err prob =0.05=0.80Power $(1-\beta \text{ err prob })$ Number of groups =2Number of measurements =4 corr among rap measures =0.5Nonsphericity correction ϵ =1

Output: Noncentrality parameter λ =11.1869844

Critical F=2.6404222

numerator df = 3.0000000

denominator df = 252 =86 Total sample size

Actual power =0.8044596

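### Protocol and SAP judge normality by different rules, and the SAP's fallback swaps its mixed ANOVA for an unadjusted test at no named time point, losing the group-by-time contrast the SAP is sized on

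*SAP*

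**What the plan says.** **Protocol, statistical method.** Two normality checks are given: "Compliance with normal distribution can be examined with the QQ Plot drawing", and "normal distribution of the data used depends on the skewness and kurtosis values being between ±3". For normally distributed data it lists independent and dependent t tests, and "when comparing more than two dependent stages, analysis of variance in repeated measurements (MIX ANOVA) will be applied", with Bonferroni follow-up if a difference is found. It gives no method for non-normal quantitative data.

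**Protocol, design features.** The sizing is for two independent groups with d = 0.5: "it was determined that there should be at least 64 people in each group, according to the calculation made using the t test".

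**SAP, biostatistics preliminary assessment.** The normality check is different: "Shapiro-Wilk normality test will be used to ensure that numerical variables comply with normal distribution". The main analysis is a mixed ANOVA, conditional on parametric assumptions. The fallback reads "In cases where the parametric test assumptions regarding the relevant test are not met, whether there is a difference between the groups" and names a Student t or Mann-Whitney test. A further sentence, "In examining whether the quantitative variables change according to the pre-test and post-test measurement time", sends within-group change to a paired t or Wilcoxon test. Every test is at 0.05.

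**SAP, sample-size output.** The sized test is "F tests - ANOVA: Repeated measures , within-between interaction", with 2 groups, 4 measurements and correlation 0.5. It gives 86 babies in total at 80.4% power.

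**The concern.** An assumption check should at most change how a question is tested. Here it changes the question. If the mixed ANOVA is kept, the arms are compared on their course over time. If it is dropped, they are compared on a single set of values, at a time the SAP does not name, and the pre-bath value and the other measurements are ignored. The paired tests look at change within each arm, and two separate within-arm results are not a comparison between arms.

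The mixed-ANOVA route names no time point either, but an overall interaction test can run without one. A t or Mann-Whitney test cannot. The fallback therefore means either one time point chosen later, which can miss a difference that sits elsewhere, or every time point tested, which raises the false-positive risk. Neither is the test behind the SAP's stated power. Because the two documents define normality differently, the same data can also lead to different analyses depending on which document is followed.

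**Working it through.** **Inputs.** From the SAP: f = 0.1275153, 2 groups, m = 4 measurements, correlation ρ = 0.5, N = 86 (43 per arm), α = 0.05. From the protocol: d = 0.5, 64 per group. Assumed: two-sided tests, first measurement pre-bath with no arm difference then, equal SDs. Correlations of 0.3 and 0.7 and the skewed distributions are also assumptions.

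**1. The plan's own figures.** λ = f²·N·m/(1−ρ) = 0.1275153² × 86 × 4 / 0.5 = 11.187. With 3 and (86−2) × 3 = 252 df, critical F = 2.6404 and power = 0.8045, as the SAP states. The protocol's 64 per group gives 80.1% for a two-sided t test at d = 0.5. Both sizings reproduce, and they are for different tests.

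**2. What f means as a difference.** If the arms differ by d SD at one of four measurements (or at all three post-bath ones), f = d√3/8, so d = 8 × 0.1275153/1.732 = 0.589. Check: 43/2 × 0.589² × 0.75/0.5 = 11.19.

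**3. Power at 43 per arm, normal data, ρ = 0.5.**

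| Test | How obtained | Power |
|---|---|---|
| Group-by-time interaction | λ = 11.187, F(3, 252) | 80% |
| Unadjusted t, time point with the difference | 0.589 × √21.5 = 2.73, df 84 | 77% |
| Unadjusted t, time point without it | no difference to detect | 5% |
| ANCOVA on pre-bath value, right time point | d/√(1−ρ²) = 0.680, df 83 | 88% |
| Joint adjusted test, difference at one post-bath time | ncp = 21.5 × 0.589² × 1.6 = 11.93, F(3, 81) | 82% |
| Joint adjusted test, difference at all three | ncp = 21.5 × 0.589² × 2.4 = 17.90 | 95% |
| Adjusted post-bath mean, all three / one only | residual variance 2/3 − 0.25 | 99% / 29% |

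ANCOVA at ρ = 0.3 and 0.7 gives 81% and 97%. With the protocol's inputs, the unadjusted t test has 80%, and ANCOVA 84%, 90% and 98% at ρ = 0.3, 0.5 and 0.7.

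**4. Skewed data (simulated, right time point).** Gamma data, skewness 1, 43 per arm, difference 0.589 SD, 4,000 runs, at ρ = 0.3/0.5/0.7:
- Mann-Whitney: 82/83/83%
- Rank ANCOVA: 85/91/97%
- ANCOVA with robust standard errors: 80/86/95%

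At skewness 2 and ρ = 0.5 (2,500 runs), these are 95–96%, 98–99% and 84%. In the four-measurement simulation at skewness 1 (3,000 runs), Mann-Whitney rejects in 83% of runs at the time point with the difference and 4.7% at another. The joint adjusted test has 79% (difference at one time) or 94.5% (all three).

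**5. Is the switch needed?** Type I error of the interaction F test, 43 and 47 per arm, skewness 0 to 2, 20,000 runs: 4.7–5.4% with equal correlations. With correlations that decay over time it is 5.8–6.5% uncorrected and 4.5–5.2% with Greenhouse-Geisser correction. Skewness of this size does not require abandoning the test.

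**6. Testing every post-bath time.** Three independent tests at 0.05 give 1 − 0.95³ = 14.3%. Simulated Mann-Whitney tests on correlated measurements give 12.5–13.6%.

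**7. The two normality rules.** Gamma data with skewness 1, 4,000 runs, excess kurtosis used, Q-Q plot not simulated: Shapiro-Wilk rejects while ±3 passes in 50% of samples at n = 43 and 81% at n = 86. For normal data this happens in about 5%.

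**The case against.** The strongest reply is that the fallback loses little. At a time point with the difference, the unadjusted t test has 77% power against 80% for the interaction test. Under skewness 1, Mann-Whitney's 83% is slightly above the joint adjusted test's 79% when the difference sits at one time. At skewness 2 it beats robust ANCOVA by more than ten points. The unadjusted test is also valid under randomisation and is the kind of test the protocol is sized on. All of this stands. It makes baseline adjustment a question of efficiency, but it leaves the missing time point and the changed contrast untouched. Rank ANCOVA exceeds Mann-Whitney in every scenario run.

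A smaller repair also exists: keep the mixed ANOVA with Greenhouse-Geisser correction and delete the switch. That would retain the sized test. It would not gain from the pre-bath value as the adjusted model does (80% against 95% when all three post-bath times differ).

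Other points on that side:
- The protocol does have a Bonferroni step, but it follows only its mixed ANOVA. The SAP gives no multiplicity step for the fallback.
- Procedure time and calming time are plausibly measured once, and for these a t or Mann-Whitney test needs no time point.
- The SAP's wording does not exclude testing change scores between arms, but it does not say so either.
- The fallback sentence offers a Student t test where parametric assumptions have failed. It may mean that the mixed ANOVA's assumptions can fail while the t test's hold, so this is only a point of clarity.
- The effect pattern is assumed. The heart-rate means in the SAP (145 to 138, and 140 to 139) show another pattern, with a 5-beat gap at the first measurement and 1 beat at the last.

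**Conclusion.** The concern holds. The normality rules differ, and the SAP's fallback compares the arms without the pre-bath value, at no named time point, and without the contrast that gives 86 babies and 80.4% power. The main harm comes from the unnamed time point: 77% power if the chosen time is the right one, 5% if it is not, and about a 13% false-positive risk if all three post-bath times are tested. Not using the pre-bath value costs about 11 points at the right time point (77% against 88% at correlation 0.5, normal data), and less where the correlation is lower.

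These are illustrations, not forecasts for this trial. They rest on a 0.589 SD post-bath difference with none before the bath, the SAP's correlation of 0.5 unless stated, and gamma-shaped skew. The textual points depend on none of these. The trial is not invalidated, but the plan should be corrected before the data are seen.

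**What to change.** Put the same text in both documents:

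1. For outcomes measured before and after the bath (the physiological parameters, and the stress score if it is taken before the bath), remove the assumption-based switch. Prespecify one between-arm analysis adjusted for the pre-bath value. Use either a baseline-adjusted repeated-measures model with robust or bootstrap standard errors or, if marked skew is expected, rank ANCOVA at a named time point. Make the choice before data are seen.
2. Name the time point or contrast that decides H1 and H2. Either keep the group-by-time contrast (in the adjusted model, the joint test of the post-bath differences) or restate the SAP's power for the contrast chosen. The results above show why this matters: the adjusted post-bath mean has 99% power if all three times differ and 29% if only one does.
3. Label within-arm pre/post tests as descriptive.
4. Keep a direct between-arm test for procedure time and calming time (H3 and H4), and for the stress score at a named time point if it has no pre-bath value.

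**Cost.** Wording in both documents, a little more analysis work, and a restated power line if the deciding contrast changes. This point asks for no change to enrolment; the difference between 64 and 47 per group is a separate matter. Outcomes already taken before and after the bath, as the SAP's pre-test and post-test wording implies, need no new measurements. The documents do not confirm a pre-bath stress score, so adjustment for H1 applies only if one is taken.

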TR Istanbul University-Cerrahpaşa ID: İstanbulUCEdu **Study Protocol: June 1, 2023** the effect of two different bathing methods on vital parameters oath stress levels in preterm babies. Clinical Trial Number: NCT06166485

WORKING PROTOCOL	
Title / Date	The effect of bathing applied in two different orders on stress level and physiological parameters in term babies / 01.06.2023
Approval of the education officer of the unit(s) where the study will be carried out.	Newborn Clinic
Name and surname of the responsible investigator, e-mail address, mobile phone, signature	Prof. dr . [name] [contact] [name]
Assistant researcher name and surname, e-mail address, mobile phone, signature	[name] [contact] [name]
Assistant researcher name and surname, e-mail address, mobile phone, signature	
Financial agreements between the sponsor, principal investigator or research site	
main purpose, Secondary purpose, if any hypothesis ( es )	Main Purpose: This study was planned to determine the effect of bathing applied in two different orders (first the body and then the head, and the classical method of washing the whole body, starting from the head) on the stress level and physiological parameters of term babies.  Hypotheses:  -H0 Stress levels and physiological parameters of babies are similar in bathing methods performed from head to toe or head to toe.  -H1. Babies' stress levels are higher when bathing in a sequence from head to toe compared to bathing where the head is left until the end.  -H2. When bathing is performed in a sequence from head to toe, the baby's physiological parameters are more negatively affected than when the bath is left from head to end.  -H3. In the bathing method in which the head is washed first, the time for babies to calm down is longer than in the method in which the head is washed last.  -H4. The procedure time in the bath where the head is left last is shorter than in the bath method where the head is washed first.

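### When the mixed ANOVA is not used, the plan names no baseline-using between-arm test to decide H2; pre-post paired tests cannot fill that gap

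*SAP*

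**What the plan says.** H2 in the protocol's hypotheses compares arms: "When bathing is performed in a sequence from head to toe, the baby's physiological parameters are more negatively affected" than when the head is left until last.

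The SAP (Biostatistics Preliminary Assessment) makes a mixed-design ANOVA its first choice, provided the parametric assumptions hold. Its sample size printout is for the within-between interaction, with four measurements. It then gives a fallback: "In cases where the parametric test assumptions regarding the relevant test are not met, whether there is a difference between the groups" is to be examined by a Student t or Mann-Whitney test. For time, it adds: "In examining whether the quantitative variables change according to the pre-test and post-test measurement time, they will be examined with" a paired t test or a Wilcoxon test. For all tests, "the probability of Type I error will be taken as α =0.05".

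The protocol (Statistical method to be applied) assigns methods by number of stages. For two, "when comparing two dependent stages, dependent t test will be applied"; for more, "when comparing more than two dependent stages, analysis of variance in repeated measurements (MIX ANOVA) will be applied". An independent t test compares the two groups.

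Neither document says whether the between-group test uses the post-bath level or the change, whether the paired tests are run within each arm, or which result decides H2.

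**The concern.** A statement that one arm is affected more needs a test that sets the two arms against each other. The interaction does that. Outside the mixed ANOVA, the plan splits the question in two: do the groups differ, and do values change over time? The second part cannot answer H2, whatever its p-value. Pulse, respiration and temperature may move with any bath, so a within-arm change says nothing about washing order.

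The gap can be reached in two ways. One is failure of the assumptions under the SAP. The other is the protocol's rule for two-stage variables, which applies even to normally distributed data. On both routes the analyst has several results at 0.05 and no rule for which one answers H2. At stake are a conclusion resting on within-arm p-values, and a weaker test than the data allow.

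**Working it through.** **1. The SAP's own figure.** The inputs are in its sample size printout: f = 0.1275153, N = 86, 4 measurements, correlation 0.5, 2 groups.
- λ = f² × N × m / (1 − ρ) = 0.1275153² × 86 × 4 / 0.5 = 11.187.
- Degrees of freedom are (2 − 1)(4 − 1) = 3 and (86 − 2)(4 − 1) = 252; critical F = 2.6404; power = 0.8045.

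All agree with the SAP. The trial is therefore sized on a test that does address H2.

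**2. SD of change.** The SAP gives heart-rate SDs of 16.44 and 12.12 (training arm, first and last) and 14.22 and 10.88 (control arm). I take r = 0.5 from the printout and treat first and last as pre and post.
- Training: √(16.44² + 12.12² − 2 × 0.5 × 16.44 × 12.12) = 14.76.
- Control: √(14.22² + 10.88² − 2 × 0.5 × 14.22 × 10.88) = 12.88.
- Pooled: √((14.76² + 12.88²)/2) = 13.85.

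**3. Two paired t tests, same true change in both arms.** With 47 per arm and two-sided 0.05, p_T and p_C are the noncentral-t powers in the two arms. P(exactly one significant) = p_T(1 − p_C) + p_C(1 − p_T).

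| Common change (bpm) | p_T | p_C | Exactly one | Training only | Control only |
|---|---|---|---|---|---|
| 0 | 5.0% | 5.0% | 9.5% | 4.8% | 4.8% |
| 1 | 7.4% | 8.2% | 14.4% | 6.8% | 7.6% |
| 2 | 14.9% | 18.1% | 27.6% | 12.2% | 15.4% |
| 3 | 27.6% | 34.6% | 43.1% | 18.1% | 25.1% |
| 4 | 44.4% | 55.0% | 50.6% | 20.0% | 30.6% |
| 5 | 62.3% | 74.1% | 44.1% | 16.2% | 27.9% |
| 6 | 77.9% | 87.8% | 28.9% | 9.5% | 19.4% |
| 7 | 88.9% | 95.4% | 14.6% | 4.1% | 10.6% |

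A between-arm test of change errs in 5% by design (4.9% in 100,000 simulated trials at 43 per arm and 4 bpm, where exactly one arm was significant in 50.4%).

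**4. Sensitivity.** The peak stays near 50% but moves: to about 4.5 to 5 bpm at r = 0.3 and about 3 bpm at r = 0.7. At 7 bpm the figure is 29.2% for r = 0.3 and 2.5% for r = 0.7.

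**5. Which between-arm test.** Assume a 6 bpm arm difference after the bath (7 − 1, the SAP's two changes), equal baselines in expectation and 47 per arm. The pooled SD of the last values is √((12.12² + 10.88²)/2) = 11.52.

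| Test | SD at r = 0.5 | Power, r = 0.3 | r = 0.5 | r = 0.7 |
|---|---|---|---|---|
| Change score t test | 13.85 | 43% | 55% | 74% |
| Post-value t test | 11.52 | 71% | 71% | 71% |
| Post value adjusted for baseline (ANCOVA) | 11.52 × √(1 − 0.5²) = 9.97 | 75% | 82% | 94% |

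ANCOVA is the strongest of the three at each correlation.

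**The case against.** The strongest reply is that the main analysis is sound. The mixed ANOVA comes first in the SAP, the sample size rests on its interaction, and the protocol also uses it beyond two stages. This stands: it would be wrong to infer that the plan tests change only by paired tests.

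A reader might also infer that significance in one arm and not in the other will be taken as support for H2. The documents contain no such rule, and do not even say that the paired tests are run by arm. The table in step 3 shows what that reading would cost if adopted; it is not an error rate of the plan.

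Nor do the documents support an error of about half the time. That is the peak, it needs a common change of 4 bpm that the SAP does not state, and it counts both directions. In a given direction the maximum is about 20% or 31%, depending on the arm. The SAP does not say which bath order its training group received, so neither direction can be matched to H2.

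Finally, a between-group test on post-bath values is a valid randomised comparison, because baselines are equal in expectation. That also stands, and at r = 0.5 such a test beats a change score. What it leaves open is that the plan neither specifies that test nor makes it decisive, and it leaves the baseline unused.

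**Conclusion.** The point holds for the routes outside the mixed ANOVA: unmet assumptions in the SAP, and two-stage variables in the protocol. There, no baseline-using between-arm test is named to decide H2, and the paired tests cannot do that work. If they were read that way, exactly one arm would be significant in about 10% to 51% of trials with no true difference between bath orders, against 5% for a between-arm test.

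The range rests on the SAP's heart-rate SDs, r = 0.5, 47 per arm, normally distributed changes, independent arms, two-sided testing (the SAP does not state sidedness) and an assumed common change of 0 to 7 bpm. The documents list no measurement times, so how many variables have only two stages is unknown. This should be corrected, but it does not undermine the first-choice analysis.

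**What to change.** State in the SAP's methods paragraph, and repeat in the protocol's statistical method section, that:

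- H2, and H1 where a pre-bath stress score exists, is decided by the group-by-time interaction of the mixed ANOVA.
- Where the mixed ANOVA is not used, or there are only two stages, it is decided by a between-arm comparison of the post-bath value adjusted for the baby's pre-bath value: ANCOVA, or a rank-based ANCOVA if assumptions fail. Report the estimate with its 95% CI.
- Within-arm pre-post results are supportive only and decide no hypothesis.

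The cost is a wording change in both documents and slightly more analysis, on the same data. The downside is that within-arm p-values lose their role in the conclusion.

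### The SAP's 80.4% power assumes four measurements per baby, but neither document lists four occasions and the SAP describes change over time only as pre-test versus post-test

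*SAP*

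**What the plan says.** **SAP, sample-size paragraph and power output.** The trial is sized with "F tests - ANOVA: Repeated measures , within-between interaction". The inputs are "Effect size f=0.1275153", two groups, four measurements, a correlation of 0.5 between repeated measures and a nonsphericity correction of 1. The output shows 3 and 252 degrees of freedom, a total of 86 and "Actual power =0.8044596". A 10% allowance for loss brings the total to 94: "The study was planned to include 47 people in each group". The heart-rate figures cited from an earlier study are a first and a last value in each arm.

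**SAP, analysis text.** The main method is a mixed-design analysis of variance if its assumptions hold. No number of occasions is attached to it. The text then gives a Student t or Mann-Whitney test for differences between groups. For change over time it says: "In examining whether the quantitative variables change according to the pre-test and post-test measurement time, they will be examined with the 'Paired t test", with Wilcoxon as the alternative.

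**Protocol, Statistical method to be applied.** The test depends on the number of stages: "when comparing two dependent stages, dependent t test will be applied, and when comparing more than two dependent stages, analysis of variance in repeated measurements", the latter labelled a mixed ANOVA. An independent t test is given for two independent groups.

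**Schedule.** The protocol lists body temperature, pulse, respiration and oxygen saturation as dependent variables, and the SAP lists them among its data collection tools. Neither says when, or how often, they are measured.

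**The concern.** The number of occasions does two jobs in this plan. It enters the noncentrality parameter and degrees of freedom behind the stated power, and under the protocol's rule it decides which test is run. The power output uses four, while the only wording about change over time is in pre/post terms with tests that take two readings.

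If fewer than four occasions are analysed, the stated 80.4% no longer follows from the SAP's own inputs.

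If there are exactly two, the protocol's rule leads to a dependent t test, which works within one arm. H2 is a claim about the difference between bathing methods. A significant change in one arm and a non-significant change in the other does not show that the changes differ. The group-by-time interaction does test that, and it is the test on which the trial was sized.

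If there are four, the paired and Wilcoxon tests as worded use only two of the readings and do not match the sizing.

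**Working it through.** **Inputs**, all from the SAP power output: f = 0.1275153, so f² = 0.0162602; alpha = 0.05; 2 groups; rho = 0.5; epsilon = 1; N = 86, or 94 if every enrolled baby is analysed. The number of measurements, m, is varied.

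**Formula** for the within-between interaction with two groups and epsilon = 1:

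- lambda = f² × N × m / (1 − rho)
- df1 = m − 1; df2 = (N − 2)(m − 1)
- power = P(noncentral F with df1, df2 and lambda exceeds the central 5% critical value)

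**Step 1: reproduce the SAP.** With m = 4 and N = 86, lambda = 0.0162602 × 86 × 4 / 0.5 = 11.187. The df are 3 and 84 × 3 = 252, the critical F is 2.640 and power is 0.8045. All four agree with the SAP output, so four measurements were really entered and the 4 is not a text-extraction error.

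**Step 2: change only m.**

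| m | lambda (N = 86) | df (N = 86) | Power, N = 86 | Power, N = 94 |
|---|---|---|---|---|
| 4 | 11.187 | 3, 252 | 80.4% | 84.2% |
| 3 | 8.390 | 2, 168 | 73.1% | 77.2% |
| 2 | 5.593 | 1, 84 | 64.7% | 68.7% |

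A rough check for m = 2 uses the change score. At rho = 0.5 the SD of a change equals the SD of a single reading, and f = 0.1275 corresponds to a difference in change of 4 × 0.1275 = 0.51 SD. With 43 babies per arm, a normal approximation gives 65.7%, close to 64.7%.

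**Step 3: vary the correlation** for m = 2, N = 86.

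| rho | Power |
|---|---|
| 0.3 | 50.6% |
| 0.5 | 64.7% |
| 0.6 | 74.3% |
| 0.7 | 85.5% |

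**Step 4: size needed with two readings.** At rho = 0.5 and the same f, N = 122 gives 79.8% and N = 124 gives 80.4%. So 124 analysed babies is the smallest even total reaching 80%, or 124 / 0.9 = 137.8, that is 138 enrolled, with 10% loss.

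**The case against.** The strongest reply is that the SAP names the mixed-design ANOVA first, with no condition on the number of stages. That is the family of test used for sizing, so analysis and power agree on the main method. The paired and Wilcoxon sentence follows a clause about failed assumptions and can be read as a fallback or a within-arm description. This stands, and it means the SAP does not rely on two-occasion tests alone. It does not supply the missing count: a mixed ANOVA on one pre and one post reading is still the m = 2 row above.

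A reader might go further and infer that the trial takes exactly two readings, so that its power is 65%. The documents do not support that. The pre/post wording gives no count, the text is a rough translation, and the only explicit count anywhere is four. The first and last values from the earlier study could be the ends of a longer series and do not set this trial's schedule. The 65% also depends on keeping f and rho fixed as m changes, and the SAP justifies neither; with rho at 0.7, two readings would give more than 80%.

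A reader might also infer that the protocol's rule removes every between-arm comparison. It does not, because both documents provide tests between two independent groups. Neither says that those tests are applied to change from baseline, so they do not by themselves restore the interaction contrast.

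Finally, the protocol asks for at least 64 per group. At N = 128, two readings give lambda = 0.0162602 × 128 × 2 / 0.5 = 8.325 and 81.7% power. The shortfall therefore applies to the SAP's sample size. The conflict between 47 and 64 per group is a separate matter.

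**Conclusion.** The point holds as an inconsistency and an omission. The stated power is correct for four analysed occasions and for no smaller number at the SAP's inputs, yet no section of either document says what those four occasions are.

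If only one pre-bath and one post-bath reading are analysed, power is about 65% at 86 babies and 69% at 94, against the stated 80.4%. Those figures assume f = 0.1275 and rho = 0.5, both held fixed. At 86 babies they run from about 51% (rho 0.3) to 86% (rho 0.7). This is a scenario and not an estimate of the trial's actual power.

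The second part does not depend on the power figure. Under the protocol's stage rule, a two-stage outcome goes to a within-arm test, and the SAP's pre/post tests are also within-arm. Neither compares change between bathing methods, which is what H2 needs.

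**What to change.** 1. State the measurement occasions for each repeated outcome. Use the same count in the protocol's statistical methods, the SAP's analysis text and the SAP's power calculation.
2. If there are four occasions, keep the power figure and replace the pre-test/post-test wording with the four-occasion mixed model. If there are two, rerun the calculation with 2 measurements and restate the power (about 65% at 86 and 69% at 94 if the SAP's f and rho are kept), giving the reason for the correlation chosen.
3. Remove the protocol's condition on the number of stages, so that the group-by-time contrast tests H2 in every case. For two readings this is the between-arm comparison of change. If assumptions fail, compare change scores between arms, for example with a Mann-Whitney test. Keep within-arm paired or Wilcoxon tests as supportive only.

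The cost is wording in both documents and at most one rerun of the power calculation. The correction itself needs no extra babies. The downside is a less favourable stated power if only two readings are taken. The sponsor would then have to choose openly between accepting it and enlarging the trial, to 124 analysed babies for 80% at the SAP's inputs.
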